#### 3.1.2 Secondary Objectives

- To determine if the difference in response to therapy between treatment arms by Month 6 differs among subjects with or without HIV infection
- To determine the impact of multiple BPG injected doses on subject compliance with study product and adherence to the corresponding scheduled visits
- To determine the incidence and manifestations of the Jarisch-Herxheimer reaction among subjects treated for early syphilis with BPG
- To collect prospective data up to Month 12 on the serological response to therapy in subjects treated for early syphilis with either BPG regimen
- To compare epidemiological characteristics of early syphilis among subjects with or without HIV infection

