#### 3.2.2 Secondary Outcome Measures

- The proportion of subjects in each treatment group with a 4-fold decline in RPR titers or seroreversion by Month 6 among subjects with or without HIV infection
- The proportion of subjects in each treatment group with a 4-fold decline in RPR titers or seroreversion by Month 12
- The proportion of subjects in each treatment group with a 4-fold decline in RPR titers or seroreversion by Month 12 among subjects with or without HIV infection
- The proportion of subjects (overall and in each treatment group) who receive all assigned doses within the assigned visit windows
- The proportion of subjects in each treatment group who report Jarisch-Herxheimer reaction manifestations (fever, intensification of rash, myalgia, and other systemic symptoms) occurring within approximately 24 hours of initial BPG administration
- Demographics, sexual history, and socio-epidemiologic characteristics at baseline and sexual history through Months 6 and 12 among subjects with or without HIV infection and overall

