## 4 STUDY DESIGN

This is a Phase 4, open-label, multicenter trial to evaluate the efficacy of a single injected dose of BPG 2.4 MU (Arm 1) compared to three successive weekly injected doses of BPG 2.4 MU (Arm 2) for treatment of early syphilis in HIV-infected and HIV-uninfected subjects. Subjects will be aged 18 years or older with untreated early syphilis (primary, secondary, or early latent as defined in prior syphilis treatment trials of the Sexually Transmitted Infections Clinical Trials Group (STI CTG)). The study will be conducted at 10 sites in the US and will enroll approximately 560 subjects to achieve 420 evaluable.

The study will involve a screening/enrollment visit and seven scheduled follow-up visits (Weeks 1 and 2, and Months 1, 3, 6, 9, and 12) over a 12-month period. At the enrollment visit, after providing informed consent, all subjects will undergo a brief sexual and medical history and a directed physical examination; all women of childbearing potential will have a urine or serum pregnancy test performed as part of qualification for study participation; all subjects will undergo phlebotomy for serological testing for syphilis and HIV according to the study and clinic protocols. All subjects who have not been tested for chlamydia and gonorrhea since last sexual activity and all subjects who have been sexually active in the past 14 days will have specimens collected for chlamydia and gonorrhea testing. Subjects will have specimens collected for other STI testing as indicated by local standard of care and subject history. All eligible subjects will be randomized to Arm 1 or Arm 2 and will receive an injected dose of BPG 2.4 MU.

Study personnel will attempt to contact subjects approximately 24 hours after Visit 1 to assess for symptoms of a Jarisch-Herxheimer reaction as described in Section 8.1. At the second and third visits (Weeks 1 and 2 of follow-up), subjects randomized to Arm 2 will receive injected doses of BPG 2.4 MU.

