At all follow-up visits, subjects will have an interval history obtained, undergo a directed physical examination, and have repeat specimens collected for STI testing (based on the subject history and clinic protocols). At all follow-up visits, subjects will undergo phlebotomy for serological testing for syphilis and serum storage. At the Month 3, Month 6, Month 9, and Month 12 follow-up visits, consenting HIV-uninfected subjects will be tested for HIV infection using a 4th generation serological test for HIV. At Visit 1, study staff will swab consenting subjects' oral cavities and primary or secondary lesions (if lesions are present per Section 5.1); see Section 8.2.2.

Safety will be measured by subject report and physical examination (including vital signs: temperature, heart rate, respiration rate, and blood pressure; and genital, rectal, oral, skin, and lymph node examinations). All AEs (including solicited reactogenicity AEs and other unsolicited AEs) will be recorded through Month 1. Safety oversight will be provided by a

Data and Safety Monitoring Board (DSMB) and site Independent Safety Monitors (ISMs) as described in Section 9.6.

While sites will perform their own serological testing as needed for subject management, serological testing to determine study outcomes and serum banking will be performed at the Central Laboratory (University of Alabama at Birmingham).

The duration of the study for each subject will be 12 months. Enrollment is expected to be completed in 36 months. For additional details on study procedures/evaluations and study schedule by study visits, see Sections 7 and 8 and Appendix A.

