### **6.4 Assessment of Subject Compliance with Study Intervention/Investigational Product**

All BPG injections will be directly observed by the administering clinician. Compliance with study product for all subjects will be defined as whether subjects receive all assigned doses within the assigned visit windows.

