#### **11.4.4.2 Secondary Efficacy Analysis**

The secondary efficacy analyses will be performed in the ITT and Evaluable analysis populations. For subjects who have received BPG through the study and subsequently require retreatment for syphilis infection (i.e., per the local clinic's standard protocols), data collected following retreatment will not be used for analyses.

For the comparison of efficacy of one dose versus three doses of BPG 2.4 MU by Month 6 in each of the HIV status subgroups, the number and proportion of subjects with serological response will be summarized overall and by treatment within each HIV status subgroup. The point estimates for the treatment-specific proportions and difference in proportions as well as corresponding 95% confidence intervals will be reported. For each HIV status subgroup, a hypothesis test will be conducted using the Farrington-Manning test at the 5% one-sided level of significance to formally compare the treatment arms.

The analyses comparing one dose versus three doses by Month 12, overall and within HIV status subgroups, will follow similarly to the above. In addition, geometric mean titers and fold declines from baseline will be summarized by time-point for each treatment group, overall and within HIV status subgroups.

For the comparison of compliance between the one dose and three dose groups, the number and proportion of subjects who receive all assigned doses within the assigned visit windows will be summarized overall and by treatment. The point estimates for the treatment-specific proportions and difference in proportions as well as corresponding 95% confidence intervals will be reported. A hypothesis test will be conducted using a Chi-square test at the 5% two-sided level of significance to formally compare the treatment arms.

Demographic, sexual history, and other characteristics of subjects will be presented overall and within HIV status subgroups at baseline and throughout follow-up. HIV status subgroups will be compared with respect to epidemiological characteristics using the Pearson Chi-square test for categorical measures and the t-test for independent samples or Wilcoxon rank sum test for continuous measures.

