 At Visit 1, record concomitant medications taken in the last 30 days before initiating BPG. At subsequent visits, record all concomitant medications taken since the last visit and update previously recorded medications as appropriate.

 Collect for subjects with known HIV infection whose medical records do not include a CD4 count in the past 30 days; at Visit 4, this is only applicable to subjects newly found to have HIV infection from Visit 1 to Visit 4 (inclusive).

 Perform for subjects who do not have a previously documented positive HIV test result using locally available tests (e.g., nucleic acid tests (NATs), antibody/antigen tests).

 At Visit 1, collect specimens at sites of exposure for screening/diagnosis of chlamydia and gonorrhea for all subjects who have not been tested since last sexual activity and for all subjects who have been sexually active in the past 14 days and for other STIs as indicated by local standard of care and subject history. At subsequent visits, collect specimens at sites of

exposure for STI testing per local standard of care and subject history.

It is optional to swab subject's oral cavity and lesions, if lesions are present. See Section 8.2.2.

 At Visit 1, administer BPG to all subjects. At Visits 2 and 3, administer BPG to subjects in Arm 2 only.

At Visit 1, collect contact information. At subsequent visits, review contact information and update if needed.

 Distribute checklist at Visit 1. Subject refers to completed checklist during Jarisch-Herxheimer assessment; see Sections 7 and 8.1.

Assess per protocol Section 8.1. If subject is not reached, assess at Visit 2.

 Assess and record all AEs/SAEs (including solicited reactogenicity AEs and other unsolicited AEs).

 At Unscheduled Visits, any of the specified evaluations that are relevant to the subject may be performed at the discretion of the site PI.

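### The planned compliance comparison measures on-schedule regimen completion, gives no between-arm comparison of attendance at Visits 2 and 3, and loses most of its content in the Evaluable population

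*Protocol*

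**What the plan says.** Section 3.1.2 of the protocol sets a secondary objective with two elements: "To determine the impact of multiple BPG injected doses on subject compliance with study product and adherence to the corresponding scheduled visits".

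Section 3.2.2 lists one outcome measure for it: "The proportion of subjects (overall and in each treatment group) who receive all assigned doses within the assigned visit windows". Section 6.4 gives that same measure the name of the first element: "Compliance with study product for all subjects will be defined as whether subjects receive all assigned doses within the assigned visit windows".

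Section 11.4.4.2 plans the analysis: "the number and proportion of subjects who receive all assigned doses within the assigned visit windows will be summarized overall and by treatment". Arm-specific proportions and their difference follow, with 95% confidence intervals, and then: "A hypothesis test will be conducted using a Chi-square test at the 5% two-sided level of significance to formally compare the treatment arms". The opening of that section places the secondary efficacy analyses in both the ITT and the Evaluable populations. Section 11.4.1 makes receipt of every assigned dose a condition of being Evaluable.

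The visit schedule is common to both arms. Section 4 places follow-up at Weeks 1 and 2 for all subjects and states: "At all follow-up visits, subjects will undergo phlebotomy for serological testing for syphilis and serum storage". Only the injection differs. Appendix A, footnote 10, reads: "At Visits 2 and 3, administer BPG to subjects in Arm 2 only". Sections 7.2.1 and 7.2.2 give the windows: Visit 2 on Day 7 to 13, and Visit 3 from 6 to 12 days after Visit 2.

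**The concern.** A one-dose subject who receives the Visit 1 injection has complied, whatever happens afterwards. A three-dose subject must also attend Visits 2 and 3 in window and be injected there. A missed Visit 2 or 3 therefore counts against the three-dose arm only, although both arms are expected at those visits.

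The objective speaks of the impact of multiple doses on adherence to visits. A completion difference reported under that objective could be taken as an effect of the extra injections on attendance, which it does not measure.

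The choice of population adds a second difficulty. Where receipt of all doses is an entry condition, a compliance analysis has already removed the subjects who missed a dose.

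**Working it through.** **Stated figures.** The protocol gives no sample size, power or expected rate for this objective. Section 11.2 gives 420 evaluable subjects and 25% not evaluable: 420 / (1 - 0.25) = 560 enrolled, or 280 per arm at 1:1. That is the ITT size used below.

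**Assumptions, since the protocol gives no attendance rates.**
- One-dose completion is 100%. It could fall short only through subjects who are randomized but not dosed.
- In-window attendance is 95% at each of Visits 2 and 3 in the three-dose arm, independent between visits, so both-visit attendance is 0.95 × 0.95 = 0.9025.
- Every three-dose subject who attends is dosed, unless stated otherwise.

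**Step 1: the planned result.** Difference (three-dose minus one-dose) = 0.9025 - 1 = -0.0975. Standard error = √(0.9025 × 0.0975 / 280) = 0.0177. The Wald 95% CI is -0.0975 ± 1.96 × 0.0177, or -13.2 to -6.3 points. One-dose attendance at Visits 2 and 3 does not enter the calculation.

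**Step 2: the attendance effect behind that one result.** Let q be one-dose attendance at both visits. The effect is 0.9025 - q, with standard error √[(0.9025 × 0.0975 + q(1 - q)) / 280].

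| q | Planned completion difference | Attendance difference (95% CI), points |
|---|---|---|
| 0.81 (0.90 per visit) | -9.75 | +9.25 (3.5 to 15.0) |
| 0.9025 (0.95 per visit) | -9.75 | 0 (-4.9 to 4.9) |
| 0.9604 (0.98 per visit) | -9.75 | -5.8 (-9.9 to -1.6) |

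The same planned result is compatible with better, equal or worse attendance in the three-dose arm.

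**Step 3: dosing and attendance can separate within the three-dose arm.** Section 5.3.3 allows further dosing to be stopped, and Section 5.3.4 asks subjects who request to stop treatment to stay on the visit schedule. If 5% of three-dose attenders stop dosing, completion is 0.9025 × 0.95 = 0.857 and the planned difference is -14.3 points. With equal attendance in the two arms, the attendance effect is still 0.

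**Step 4: the Evaluable population.** Let f be the share of the 9.75% non-compliant three-dose subjects who missed a dose altogether. The rest were dosed out of window. Assume that the other Evaluable criteria are unrelated to compliance. Evaluable compliance in the three-dose arm is then 0.9025 / (1 - 0.0975f).

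| f | Evaluable compliance, three-dose | Difference from one-dose (100%) |
|---|---|---|
| 0 | 0.9025 / 1 = 90.25% | -9.75 points |
| 0.5 | 0.9025 / 0.95125 = 94.9% | -5.1 points |
| 1 | 0.9025 / 0.9025 = 100% | 0 |

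The ITT difference is -9.75 points in every row. The Evaluable difference lies nearer zero whenever any dose is missed. Section 11.4.4.1 keeps subjects who responded before meeting an Evaluable exclusion, but it words this for the response analyses. If it were carried over, it would readmit some dose-missers selected on outcome.

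**The case against.** The strongest reply is that the corresponding visits are most naturally the visits that go with the doses. On that reading the in-window requirement makes the outcome a composite of dosing and attendance. The one-dose arm's only such visit is Visit 1, and comparing a three-visit course with a one-visit course is a legitimate meaning of the impact of multiple doses. This stands in large part: the planned measure is valid for on-schedule completion and captures dosing-visit attendance in the three-dose arm. A reader might infer that the adherence element of the objective is left wholly unanswered, but the documents do not support that. What remains is that the one-dose arm supplies no attendance comparison, although the same visits are scheduled there.

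A reader might also infer that the chi-square test has an inflated false-positive rate, because it tends to reject when attendance is equal. It does not. Completion truly differs between the arms in that setting, so rejection is power against a real difference. The error would lie in reading it as an attendance effect.

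The statistical analysis plan is not at hand, and Section 11.4 leaves detail to it. An attendance table may appear there. But the protocol itself fixes the outcome list, the compliance definition, the test and the populations.

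On the population, ITT is already planned alongside Evaluable, and Evaluable does not require doses to be in window. The Evaluable analysis is therefore not void. It is uninformative about missed doses.

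**Conclusion.** The point holds as a modest one about a secondary analysis. The planned difference describes on-schedule regimen completion. It does not estimate an effect of multiple doses on attendance at Visits 2 and 3: under the assumed rates, one planned difference of -9.75 points fits attendance effects from +9.25 to -5.8 points. In the Evaluable population compliance can fail only on timing, and the difference is biased toward zero, in the example to somewhere between -9.75 and 0 points depending on how many failures are missed rather than late doses.

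The sizes rest on assumed attendance rates, independence between visits and near-complete dosing in the one-dose arm. The direction rests only on the definitions in Sections 6.4, 11.4.1 and 11.4.4.2. Section 11.1 makes secondary p-values informational, and the primary conclusion and the sample size are not touched.

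**What to change.** 1. Run the compliance comparison in ITT only, and remove it from the Evaluable population.
2. Keep the dose-completion proportions and their difference with its confidence interval, labelled as on-schedule regimen completion and not as visit adherence. The chi-square test may stay as informational. State in Section 3 which visits the objective means.
3. Add one ITT secondary table by arm: in-window attendance at Visit 2, and at both Visits 2 and 3, with risk difference and 95% CI. A missed Visit 2 counts as not attending both. Because the Visit 3 window runs from Visit 2, report Visit 3 alone either among Visit 2 attenders or against an analysis window stated for subjects who missed Visit 2.
4. State how subjects whom the protocol itself takes out before Visit 3 are counted (retreatment under Section 5.3.3, pregnancy under Section 9.3.3), for example reported separately with a sensitivity analysis.

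The cost is some wording and one extra informational table. Both arms already have these visits and their study procedures on the schedule, so no new visit or procedure is needed.

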#### **11.4.4.3 Exploratory Efficacy Analysis**

Any exploratory or sensitivity analyses to be performed to support any of the primary or secondary objectives will be specified in the Statistical Analysis Plan. As an example, the following alternative serological response classifications will be explored:

- Response: 4-fold decline in RPR titer compared to baseline, or RPR-negative (i.e., seroreversion).
- Non-Response: Less than 4-fold decline in RPR titer compared to baseline, and RPR-positive
- Failure: 4-fold or greater increase in RPR titer without a clear history of re-exposure

A blinded case review committee will review subjects' data to determine cases of re-exposure. If a subject has an observed serological response prior to meeting one of the Evaluable analysis population exclusion criteria, the subject will be included in the analyses as a responder. For subjects who have received BPG through the study and subsequently require retreatment for syphilis infection (i.e., per the local clinic's standard protocols), data collected following retreatment will not be used for analyses.

## **12 SOURCE DOCUMENTS AND ACCESS TO SOURCE DATA/DOCUMENTS**

Each participating site will maintain appropriate medical and research records for this trial, in compliance with ICH E6, Section 4.9, and regulatory and institutional requirements for the protection of confidentiality of subjects. Each participating site will permit authorized representatives of DMID, its designees, and appropriate regulatory agencies to examine (and when required by applicable law, to copy) clinical study records for the purposes of quality assurance reviews, audits, monitoring, and evaluation of the study safety and progress. These representatives will be permitted access to all source data, which include, but are not limited to, hospital records, clinical and office charts, laboratory notes, memoranda, evaluation checklists, pharmacy dispensing records, recorded data from automated instruments, copies or transcriptions certified after verification as being accurate and complete, microfiches, photographic negatives, microfilm or magnetic media, x-rays, and subject files and records kept in the pharmacies, laboratories, and medico-technical departments involved in this clinical trial. Source data are all information, original records of clinical findings, observations, or other activities in a clinical trial necessary for the reconstruction and evaluation of this trial.

## **13 QUALITY CONTROL AND QUALITY ASSURANCE**

Following a written DMID-accepted site quality management plan, the participating site is responsible for conducting routine quality assurance (QA) and quality control (QC) activities to internally monitor study progress and protocol compliance. The site PI will provide direct access to all trial-related sites, source data/data collection forms, and reports for the purpose of monitoring and auditing by the sponsor, and inspection by local and regulatory authorities. The site PI will ensure all study personnel are appropriately trained and applicable documentations are maintained on site.

The Statistical and Data Coordinating Center (SDCC) will implement QC procedures beginning with the data entry system and generate data QC checks that will be run on the database. Any missing data or data anomalies will be communicated to the site(s) for clarification and resolution.

## **14 ETHICS/PROTECTION OF HUMAN SUBJECTS**

### **14.1 Ethical Standard**

The site PI will ensure that this trial is conducted in full conformity with principles of the Belmont Report: Ethical Principles and Guidelines for the Protection of Human Subjects of Research of the National Commission for the Protection of Human Subjects of Biomedical and Behavioral Research (April 18, 1979) and codified in 45 CFR 46, 21 CFR 50 and 56, and ICH E6; 62 Federal Regulations 25691 (1997), if applicable. The site PI's institution will hold a current Federal Wide Assurance (FWA) issued by the Office of Human Research Protection (OHRP) for federally funded research.

### **14.2 Institutional Review Board**

Prior to enrollment of subjects into this trial, the approved protocol and ICF will be reviewed and approved by the appropriate IRB listed on its FWA.

The responsible official for the IRB will sign the IRB letter of approval of the protocol before the start of this trial, and provide a copy to DMID. The IRB FWA number will be provided to DMID.

Should amendments to the protocol be required, the amendments will be written by the sponsor and provided to the site PI for submission to the IRB.

### **14.3 Informed Consent Process**

The site PI, or designated study staff, will choose subjects in accordance with the eligibility criteria detailed in Section 5. Before any study procedures are performed, subjects must sign an ICF that complies with the requirements of 21 CFR Part 50, 45 CFR Part 46, and the local IRB.

Informed consent is a process that is initiated prior to an individual agreeing to participate in a trial and continuing throughout the individual's trial participation. Before any study procedures are performed, subjects will receive a comprehensive explanation of the proposed study procedures and study drug, including the nature and risks of the trial, alternate therapies, any known AEs, the investigational status of the components, and the other elements that are part of obtaining proper informed consent. Subjects will also receive a detailed explanation of the proposed use and disclosure of their protected health information, including specifically their specimens. Subjects will be allowed sufficient time to consider participation in the trial, after having the nature and risks of the trial explained to them, and will have the opportunity to discuss the trial with their family, friends, or legally authorized representative or think about it prior to agreeing to participate.

ICFs describing in detail the study drug, study procedures, risks, and possible benefits are given to subjects. The ICF must not include any exculpatory statements. ICFs will be IRB-approved, and subjects will be asked to read and review the appropriate document. Upon reviewing the appropriate document, the site PI (or designee) will explain the research study to subjects and answer any questions that may arise. Subjects must sign the ICF, and written documentation of the informed consent process is required prior to starting any study procedures/interventions being done specifically for the trial, including administering BPG.

DMID will provide the site PI, in writing, any new information that significantly affects the subjects' risk of receiving BPG. This new information will be communicated by the site PI to subjects who consent to participate in the trial in accordance with IRB requirements. The ICF will be updated, and subjects will be re-consented per IRB requirements, if necessary.

Study personnel may employ IRB-approved recruitment efforts before obtaining the subject's consent; however, before any study procedures are performed to determine protocol eligibility, an ICF must be signed. Subjects will be given a copy of all ICFs that they sign.

By signing the ICF, subjects agree to complete all evaluations required by the trial, unless the subject withdraws voluntarily or is terminated from the trial for any reason.

The rights and welfare of subjects will be protected by emphasizing to subjects that the quality of their medical care will not be adversely affected if they decline to participate in or withdraw from this trial.

